10.1.5 Day 1 and Day 8 (Telephone Contact)

The post-vaccination phone contacts will be performed by blinded site staff members. The following procedures will be performed during the phone contact (acceptable interval of + 1 day for Day 1 and + 1 day for Day 8):

- Ask the subjects about any difficulties in recording their data, any change in health, any
 visits to health care facilities and/or medical practitioners, and any use of concomitant
 medications. Record the information in the source documents;
- For any unsolicited AEs and/or solicited local and systemic AEs of greater than Grade 2 (moderate), the Investigator should be informed within 48 hours of the time the clinical site is made aware of the event. The Investigator may request that the subject return to the clinic for evaluation;

- Advise subjects to immediately contact the Investigator (or his/her designee) in the event of any AE that requires medical attention. Subjects will be provided with a phone contact number and be instructed to call if any suspected reaction to the vaccination is felt to be significant or of concern;
- Instruct the subjects to contact the clinical site immediately in case they were tested positive for COVID-19;
- Remind the subjects how to measure and record any solicited local and systemic AEs. Subjects should also be reminded to record any changes in health, including changes in AEs and changes in medications;
- Remind subjects of their next appointment (date and time) for the clinical visit and/or the next phone contact. Subjects will also be reminded to record their data in their diary and memory aid in a timely manner.

In the event that a subject cannot be reached via phone, he/she may be contacted by text message or via email (if these contacts are available). However, the phone should be the initial and preferred means of communication. At least three attempts within allowed time window should be made in order to reach the subject.

10.1.6 Day 3 Follow-up (Visit 3)

The post-vaccination follow-up visit procedures will be performed by blinded site staff members at the clinical site. For subjects in quarantine, these procedures will be performed by blinded trained medical staff at the subject's home (or place of quarantine). The following procedures will be performed during the Day 3 visit (\pm 1 day):

- Perform a vital signs measurement, including resting BP, HR, and OT;
- Perform a history- or symptom-directed physical examination. The physical exam will be performed by the Investigator or sub-Investigator;
- Collect blood samples for biochemistry and haematology;
- Perform urinalysis on all subjects;
- Review the diary and memory aid content with the subject to ensure appropriate completion. Corrections must be made by the subject him/herself and all corrections must be initialed and dated;
- Review the subject's safety data and ensure all updates on concomitant medication usage and any changes in the subject's health (AEs, SAEs, AESIs, MAAEs, or NOCDs) are recorded appropriately;
- Advise the subjects to immediately contact the Investigator or his/her designee, in the event of any AE that requires a visit to an emergency room and/or hospitalization;
- Instruct the subjects to contact the clinical site immediately in case they were tested positive for COVID-19;
- Remind the subjects of their next phone contact (date and time).

10.1.7 Day 28 (Visit 4)

The post-vaccination follow-up visit procedures will be performed by blinded site staff members at the clinical site. For subjects in quarantine, these procedures will be performed by blinded trained medical staff at the subject's home (or place of quarantine). For all subjects a safety follow-up will be performed on or shortly after Day $28 (\pm 2 \text{ days})$:

- Perform a vital signs measurement, including resting BP, HR, and OT;
- Perform urinalysis on all subjects;
- Collect blood samples for biochemistry and haematology;
- Collect blood samples for immunogenicity (serology) assessments and prepare and store these samples until shipment to the analytical laboratories.
- Review the diary and memory aid content with the subject to ensure appropriate completion. Corrections must be made by the subject him/herself and all corrections must be initialed and dated. Collect manual diary and memory aid and provide subjects with just a memory aid for the collection of safety data from Day 29 to Day 182;
- Review the subject's safety data and ensure all updates on concomitant medication usage and any changes in the subject's health (AEs, SAEs, AESIs, MAAEs, or NOCDs) are recorded appropriately;
- Advise the subjects to immediately contact the Investigator or his/her designee, in the event of any AE that requires a visit to an emergency room and/or hospitalization;
- Provide appointments (date and time) for the next telephone contacts and the next planned visit to the clinical site (Day 182).

10.1.8 Monthly Calls Thereafter (Telephone Contact)

Subjects should be contacted by telephone once every month (every 30 days \pm 14 days; Day 28 visit date as starting reference). The post-vaccination monthly phone contacts will be performed by blinded site staff members. The following procedures will be performed during the phone contacts:

- Ask the subjects about any change in health (AEs ongoing from Day 28, SAEs, AESIs, MAAEs, or NOCDs), any visits to health care facilities, and/or medical practitioners and use of any concomitant medications. Record the information in the source documents;
- Advise the subjects to immediately contact the Investigator (or his/her designee), in the event of any AE which require a visit to the emergency and/or hospitalization;
- Instruct the subjects to contact the clinical site immediately in case they were tested positive for COVID-19;
- Remind the subjects of their next appointment (date and time) for the next telephone contact and/or the next planned visit to the clinical site (Day 182 or Day 365);
- Inform the subjects that during the subsequent visit to the clinical site, they will be questioned regarding any events that may have occurred since the last contact.

In the event that a subject cannot be reached via telephone, he/she may be contacted by text message or via email (if these contacts are available). However, the telephone should be the initial and preferred means of communication. At least three attempts within allowed time window should be made in order to reach the subject.

10.1.9 Day 182 (Visit 5)

For some subjects, the Day 182 visit may occur during the time the subject may want to receive the 2021-2022 seasonal influenza vaccine. Hence, the tests/procedures (including immunogenicity sample collection) originally planned for the Day 182 visit will be collected at the Day 182 timepoint or immediately prior to administration of the 2021-2022 seasonal influenza vaccine (whichever comes first).

The post-vaccination visit procedures will be performed by blinded site staff members at the clinical site. For subjects in quarantine, these procedures will be performed by blinded trained medical staff at the subject's home (or place of quarantine). The following procedures will be performed during the Day 182 visit (± 14 days):

- Review the memory aid content with the subject to ensure appropriate completion.
 Corrections must be made by the subject him/herself and all corrections must be initialed and dated. Collect manual memory aid and provide subjects with another memory aid for the collection of safety data from Day 183 to Day 365;
- Review the subject's safety data and ensure all updates on concomitant medication usage and any changes in the subject's health (AEs ongoing from Day 28, SAEs, AESIs, MAAEs, or NOCDs) are recorded appropriately;
- Confirm that the subject has continued to comply with protocol requirements (e.g. no use of prohibited concomitant medications);
- Perform a vital signs measurement, including resting BP, HR, and OT;
- Collect blood samples for immunogenicity (serology) assessments and prepare and store these samples until shipment to the analytical laboratories.

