5.4 Prohibited Therapy

The following medications or therapies are prohibited during the conduct of this study:

- 1. Administration of any non-influenza vaccine (excluding authorized COVID-19 vaccines) up to blood sampling on Day 28 of the study. Immunization on an emergency basis during the study will be evaluated on case-by-case basis by the Investigator;
- 2. Administration of any adjuvanted or investigational influenza vaccine (other than the study vaccine) up to completion of the study;
- 3. Use of any investigational or non-registered product during the study period. Subjects may not participate in any other investigational or marketed drug study while participating in this study until after the study;
- 4. Administration of any medication or treatment that may alter the vaccine immune responses, such as:
 - Systemic glucocorticoids at a dose exceeding 10 mg of prednisone (or equivalent) per day for more than seven consecutive days or for 10 or more days in total;
 - Cytotoxic, antineoplastic, or immunosuppressant drugs;
 - Any immunoglobulin preparations or blood products, or blood transfusion;
- 5. Use of prophylactic medications (e.g. antihistamines [H1 receptor antagonists], nonsteroidal anti-inflammatory drugs [NSAIDs], systemic and topical glucocorticoids, non-opioid and opioid analgesics) for seven days post-vaccination to prevent or pre-empt symptoms due to vaccination;
- 6. Use of any prescription antiviral drugs with the intention of COVID-19 prophylaxis, including those that are thought to be effective for prevention of COVID-19 but have not been licensed for this indication, during the study.

If one of the first five criteria is met by a subject during the study (after vaccination), the subject may still remain in the study however the inclusion of the subject's data within the PP set, ITT set, or SAS may be impacted.

Given that an important objective of this study is to evaluate the tolerability of the study vaccine, the use of prophylactic medications to prevent or pre-empt symptoms due to vaccination is specifically prohibited up to Day 7 (end of collection of solicited symptoms). A prophylactic medication is a medication administered in the absence of ANY symptom and in anticipation of a reaction to the vaccination (e.g. an antipyretic is considered to be prophylactic when it is given in the absence of fever or any other symptoms, to prevent fever from occurring, vitamins used to boost immune system, etc.).

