10.1.10 Final Visit – Day 365 (Visit 6)

The post-vaccination final visit procedures will be performed by blinded site staff members at the clinical site. For subjects in quarantine, these procedures will be performed by blinded trained medical staff at the subject's home (or place of quarantine). The following procedures will be performed during the Day $365 \text{ visit } (\pm 14 \text{ days})$:

- Review the subject's safety data and ensure all updates on concomitant medication usage and any changes in the subject's health (AEs ongoing from Day 28, SAEs, AESIs, MAAEs, or NOCDs) are recorded appropriately. Collect the subject's memory aid;
- Confirm that the subject has continued to comply with protocol requirements (e.g. no use of prohibited concomitant medications);
- Perform a vital signs measurement, including resting BP, HR, and OT;

• Collect blood samples for immunogenicity (serology) assessments and prepare and store these samples until shipment to the analytical laboratories.

Any subject who withdraws consent from the study will be asked to undergo Day 365 visit (Visit 6) procedures within two weeks of withdrawal, if the subject agrees.

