### 4.4.3. Intent-to-Treat (ITT) Set

The ITT set will consist of all subjects who were randomized in the study. Subjects who received the wrong treatment will be analyzed as randomized.

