### 4.4.4. Per Protocol (PP) Sets

Four individual per protocol (PP) sets will be defined which will consist of a subset of subjects with no major protocol deviations related to subject eligibility, the ability to develop a valid immune response, prohibited medication use, or the immunogenicity analyses; and who received QVLP or the active comparators. Only protocol deviations up to the visit of interest will be observed for each PP set. In particular, immunogenicity assessments should be available on certain visits, as follows:

- Per Protocol Set 1: Day 0,
- Per Protocol Set 2: Day 0 and Day 28,

Confidential

Medicago USA Page 22 of 55

- Per Protocol Set 3: Day 0 and Day 182,
- Per Protocol Set 4: Day 0 and Day 365.

Subjects who had blood samples for immunogenicity taken outside of the time window for blood sample collection at Day 0 or the respective visit (Day 28 / Day 182 / Day 365) are to be excluded from the PP set for the specific visit. Major protocol deviations will be identified and documented by Medicago during a blinded data review prior to database lock and confirmed at the time of database lock. Assignment of subjects to each of the PP sets (yes/no) will be provided to CCI Subjects who received the wrong treatment, but for whom the treatment received can be unequivocally confirmed, will be analyzed as treated, provided they have no other deviations that compromise their data. For analyses using the Per Protocol set, subjects will be analyzed according to the vaccines actually received.

Medicago USA Page 23 of 55

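### No pre-specified rule covers Day 365 HI titers drawn after a foreseen 2021-2022 seasonal influenza vaccine, so within-arm 12-month persistence can be overstated and the PP/ITT comparison would not show it

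*Protocol*

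**What the plan says.** **Revaccination is foreseen.** Protocol 10.1.9 states: "For some subjects, the Day 182 visit may occur during the time the subject may want to receive the 2021-2022 seasonal influenza vaccine". Table 1 footnote 10 repeats this. Both respond by taking the Day 182 procedures, including the immunogenicity sample, at Day 182 or just before that vaccine, whichever is earlier.

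**Day 365 has no such step.** Protocol 10.1.10 says only: "Collect blood samples for immunogenicity (serology) assessments and prepare and store these samples until shipment to the analytical laboratories". It also asks sites to confirm that no prohibited medication was used.

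**Prohibited therapy (Protocol 5.4, repeated in SAP 6.5).** The item on influenza vaccines reads "Administration of any adjuvanted or investigational influenza vaccine (other than the study vaccine) up to completion of the study". A separate, open-ended item bars "Administration of any medication or treatment that may alter the vaccine immune responses"; its examples are glucocorticoids, cytotoxic or immunosuppressant drugs, and immunoglobulins or blood products. If one of the first five items is met, the subject may stay in the study, but inclusion of the subject's "data within the PP set, ITT set, or SAS may be impacted".

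**Analysis sets.** SAP 4.4.4 gives "Per Protocol Set 4: Day 0 and Day 365" as the sampling requirement and admits subjects with "no major protocol deviations related to subject eligibility, the ability to develop a valid immune response, prohibited medication use, or the immunogenicity analyses". Major deviations are settled by the sponsor in a blinded review before database lock. SAP 4.4.3 says: "The ITT set will consist of all subjects who were randomized in the study". ITT is the only sensitivity analysis stated for immunogenicity (SAP 4.4). SAP 4.3 uses all observed data where appropriate.

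**Endpoint.** Persistence of homologous HI titers at 6 and 12 months is a secondary objective (Protocol 2.2). SAP 8.2 analyses Day 365 GMT, GMFR, SC and SP by the primary method and does not mention revaccination.

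**The concern.** A persistence result should describe what remains of the response to the study vaccine. The plan recognises that a new seasonal vaccine would disturb this at six months and guards that sample. The same vaccine can precede the later sample, which has no guard. For a subject whose Day 182 draw is brought forward because of the vaccine, the Day 365 draw necessarily follows it.

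To the extent that the 2021-2022 vaccine raises HI titers to the 2020-2021 study strains, the 12-month figures mix two responses. The bias is upward in every arm. Both analysis sets share it, so agreement between PP and ITT could be misread as support for the persistence estimate.

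**Working it through.** **1. Does any rule catch the vaccine?**

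| Provision | Covers a licensed unadjuvanted seasonal vaccine before Day 365? |
|---|---|
| Protocol 5.4 item 1 | No: non-influenza vaccines, to the Day 28 sample |
| Protocol 5.4 item 2 | No: adjuvanted or investigational products only |
| Protocol 5.4 item 4 | Unclear: open-ended, but no vaccine among its examples, and influenza vaccines have their own item |
| SAP 4.4.4 deviation categories | Discretionary: not named, and a vaccine the protocol foresees is not said to be a deviation |
| SAP 4.4.3 ITT | No: all randomized |
| SAP 8.2 | No flag, exclusion or sensitivity analysis |

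**2. Can Day 365 draws fall after the vaccine?** Protocol 12 places SAP finalization before first screening, and SAP version 1.0 is dated 19 Oct 2020. A subject dosed that day has Day 365 on 19 Oct 2021, with the window opening on 5 Oct 2021. Dosing on 15 Jan 2021 (28 days before the 12 Feb 2021 data transfer in SAP 10) gives 15 Jan 2022. Dosing on 8 Mar 2021, the date of protocol version 4.0, gives 8 Mar 2022, and SAP 4.2.1 plans enrollment after that version took effect. If the 2021-2022 vaccine is given mainly in autumn 2021 (assumption), the earliest subjects are less exposed and the later ones more so.

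**3. Size within an arm.** The documents give neither uptake nor boost. Let a proportion p be revaccinated before the draw, with titers multiplied by B at Day 365. Day 0 is unaffected, so mean log fold rise shifts by p × log B and GMT and GMFR are multiplied by B^p.

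| B | p = 10% | 30% | 50% | 70% |
|---|---|---|---|---|
| 1 | 1.00 | 1.00 | 1.00 | 1.00 |
| 1.5 | 1.04 | 1.13 | 1.22 | 1.33 |
| 2 | 1.07 | 1.23 | 1.41 | 1.62 |
| 3 | 1.12 | 1.39 | 1.73 | 2.16 |

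Seroprotection, assuming log-normal titers with true Day 365 GMT 20 and SD 0.5 log10: the proportion at or above 40 is 27.4%. At B = 2 it is 50% among the revaccinated. The reported rate is (1 − p) × 27.4% + p × 50%, or 33.0 / 38.7 / 44.3% at p = 25 / 50 / 75%.

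**4. Would PP against ITT show it?** Simulation with 40 per arm, 10% unrelated PP exclusions, SD 0.5 log10 and B = 2: the PP GMT is inflated 1.19 / 1.42 / 1.69-fold at 25 / 50 / 75% uptake, while the ITT/PP ratio stays at 1.00.

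**5. Arm ratios.** With common B and equal uptake the factor B^p cancels. If uptake differs by 10 or 20 points at B = 2, the ratio is multiplied or divided by 2^0.1 = 1.07 or 2^0.2 = 1.15. If revaccinated subjects in both arms converge to the same GMFR (say 4), a true ratio of 2.0/1.5 = 1.33 becomes 1.33^(1 − p) = 1.30 / 1.22 / 1.15 / 1.09 at p = 10 / 30 / 50 / 70%.

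**6. Precision if such titers are excluded.** The Tukey 95% CI factor for an arm ratio is 10^(q × SD/√n). SAP 4 analyses the five stopped groups alongside the other three, and the code in SAP 13.3 adjusts over all levels of treatment, so q is for eight groups. The size of the stopped groups is not given; it was varied from 3 per group up to the same n as the main arms. SD 0.5 log10 is assumed.

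| n per arm (share excluded) | 8 groups | 3 groups only |
|---|---|---|
| 40 (0%) | about 2.2 | 1.84 |
| 28 (30%) | about 2.6 | 2.08 |
| 20 (50%) | about 3.1 | 2.40 |
| 12 (70%) | 4.3 to 4.5 | 3.17 |

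**The case against.** The strongest reply is that the blinded review already has the means. It can treat a seasonal vaccine as a deviation bearing on the immunogenicity analyses, or read it into the open-ended item on treatments that alter immune responses. This stands in part. A reader might infer that PP Set 4 and ITT are certain to keep these titers, but the documents do not go that far. What they lack is a stated rule. Leaving the matter to case-by-case review of a vaccine the protocol itself anticipates is not pre-specification, which SAP 1 gives as the SAP's purpose. Recipients of an adjuvanted seasonal product could be dropped from PP but not ITT, so the two sets might differ for that part.

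A reader might also infer that the vaccine will go unrecorded, because Protocol 5.3 and Table 1 footnote 5 list vaccines that the protocol does not foresee. That is too strong. The phrase may simply mean any vaccine other than study treatment, and monthly calls, memory aids and the Day 365 medication review should bring it to light. It remains unclear whether the vaccine and its date must be entered in the eCRF.

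It is also fair that analysing all observed data is legitimate, that excluding revaccinated subjects conditions on a post-randomization choice, and that this is one secondary timepoint. Protocol 12.3 and SAP 10 tie next-study design decisions to the Day 28 and Day 182 analyses. These points limit the severity and argue for showing both versions.

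**Conclusion.** The concern holds as a gap in pre-specification. Unless review discretion is used, both analysis sets keep Day 365 titers drawn after a licensed unadjuvanted seasonal vaccine, and within-arm persistence can be overstated. At an assumed residual boost of 2, GMFR is inflated by 7% to 62% over 10% to 70% uptake; at B = 1 there is no bias. Neither uptake nor boost comes from the documents.

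A reader might infer that the treatment comparisons are biased too. The documents do not support that in general: arm ratios change only with unequal uptake or converging titers. The Day 28 primary endpoint is unaffected. The gap should be fixed, but it does not threaten the main result.

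A reader might further infer that an early pre-vaccine Day 182 draw is lost from Per Protocol Set 3 as out of window. Table 1 footnote 10 may be meant to widen that window, so this is only a matter for clarification.

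**What to change.** In SAP 4.4.4 and 8.2, before database lock:

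1. Derive a flag and date for any non-study influenza vaccine received before the Day 365 sample.
2. Report Day 365 GMT, GMFR, SC and SP with all observed data, and again excluding titers drawn after such a vaccine. State in advance which version supports the persistence statement.
3. Tabulate the number revaccinated by arm, with timing relative to the Day 365 draw.
4. Confirm that a seasonal influenza vaccine after Day 28 and its date are entered in the eCRF; otherwise query sites.
5. As a clarification, reconcile Protocol 10.1.9 and Table 1 footnote 10 with the out-of-window exclusion in Protocol 12.1.3 and SAP 4.4.4.

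The cost is SAP wording, one derived variable, one extra set of Day 365 tables, and an eCRF check or site query. The excluding version has fewer, self-selected subjects and wider intervals (step 6 of the working), so neither version should stand alone.

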10.1.10 Final Visit – Day 365 (Visit 6)

The post-vaccination final visit procedures will be performed by blinded site staff members at the clinical site. For subjects in quarantine, these procedures will be performed by blinded trained medical staff at the subject's home (or place of quarantine). The following procedures will be performed during the Day $365 \text{ visit } (\pm 14 \text{ days})$:

- Review the subject's safety data and ensure all updates on concomitant medication usage and any changes in the subject's health (AEs ongoing from Day 28, SAEs, AESIs, MAAEs, or NOCDs) are recorded appropriately. Collect the subject's memory aid;
- Confirm that the subject has continued to comply with protocol requirements (e.g. no use of prohibited concomitant medications);
- Perform a vital signs measurement, including resting BP, HR, and OT;

• Collect blood samples for immunogenicity (serology) assessments and prepare and store these samples until shipment to the analytical laboratories.

Any subject who withdraws consent from the study will be asked to undergo Day 365 visit (Visit 6) procedures within two weeks of withdrawal, if the subject agrees.

